Sleep, Hypertension, and Nocturia: Multicomponent Approach for Comorbid Illnesses

University of Pittsburgh STUDY21050132

NCT05419830

Protocol Date: September 1, 2021

INTRODUCTION

Elevated nighttime blood pressure (BP), poor sleep, and nocturia are comorbid, mutually exacerbating conditions. Both elevated nighttime systolic blood pressure (SBP), and poor sleep disrupt the diurnal pattern of urine excretion by increasing nighttime sodium (natriuresis) and water (diuresis) excretion leading to increased nighttime urine production causing nocturia. This increased frequency nighttime awakenings with nocturia, in turn, contributes to poor sleep and elevated nighttime SBP. We postulate that treatments targeted towards these etiologies will help break this vicious cycle.

Traditionally, antihypertensive medications are dosed in the morning targeting daytime BP. However, some research suggests that nighttime BP best predicts risk for major cardiovascular events. Several clinical trials of bedtime dosing of BP medication—chronotherapy—show better nighttime BP control. However, no clinical studies have considered or tested chronotherapy as a treatment for nocturia. With respect to poor sleep, we have shown that brief behavioral treatment of insomnia (BBTI) significantly improves not only sleep but also self-reported nocturia among the elderly. Therefore, we envision a multicomponent approach with chronotherapy (bedtime dosing of certain antihypertensives) and behavioral sleep intervention (BBTI) to concurrently address the prevalent and chronic, mutually exacerbating conditions: nocturia, poor sleep, and hypertension.

STUDY OVERVIEW

This pilot study will provide critical preliminary data regarding the relation between sleep and nighttime BP in seniors. In the proposed pilot study 30 community-dwelling older adults (aged >65) who take at ≥ 1 daily non-diuretic antihypertensive medication, have a mean SBP >135 mm Hg, and awaken ≥ 2 times nightly to void will be randomly assigned to one of the 3 groups of 10 participants each to 1) morning (am) HTN medication dosing, 2) BBTI with am HTN medication dosing, 3) nighttime non-diuretic HTN medication dosing (chronotherapy) for 6 weeks. At baseline and 6 weeks, participants will undergo 48-hour ambulatory BP monitoring, in-home sleep study, complete a 3-day bladder diary. Data from this study will provide feasibility and pilot data for a subsequent, larger, and more definitive trial.

Outcome measures:

- 1) Change in mean sleep time systolic BP dip pre- vs post-intervention- measured by 24-hour ambulatory BP monitor (ABPM)
- 2) Change in nocturia frequency as determined by 3-day bladder diary
- 3) Change in nocturnal polyuria measured by NPI- nocturnal polyuria index=(nocturnal urine volume/24-hour volume)*100
- 4) Change in global Pittsburgh Sleep Quality Index (PSQI) scores pre- vs post-intervention

Data Analysis:

In this pilot investigation, we will perform descriptive and graphical analyses as well as inferential analyses. As appropriate for a pilot study, we will focus on the magnitude of effects rather than on the *p*-values.

First, we will compare baseline characteristics between the 3 groups using analysis of variance (ANOVA), Kruskal-Wallis, chi-square and Fisher's exact tests, as appropriate. Any significant differences will be used as additional covariates in sensitivity analyses. Second, we will fit a series of analysis of covariance (ANCOVA) models using the SAS® GLM procedure with pre- to post-intervention change in each continuous outcome as the dependent variable: BBTI (yes/no), chronotherapy (yes/no) and baseline value of outcome as independent variables. Third, we will construct means contrasts appropriate for testing the hypotheses. Magnitude of the estimate and/or its statistical significance of: BBTI vs usual care and chronotherapy vs usual care contrasts will be interpreted as a test of hypothesis 1.1. Finally, we will add changes in measures of sleep (decrease in WASO) and % of deep sleep to the above model as an additional independent variable and notice the reduction in magnitude of the above means contrasts.

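### The last analysis step looks for smaller treatment contrasts after adding sleep changes, with no measure of uncertainty; the contrasts can change without any mediation by sleep (minor)

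*Combined protocol and SAP*

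**What the plan says.** The Data Analysis section fits an ANCOVA of change in each continuous outcome on BBTI, chronotherapy and the baseline value. The "BBTI vs usual care and chronotherapy vs usual care contrasts will be interpreted as a test of hypothesis 1.1". As the final step, "we will add changes in measures of sleep (decrease in WASO) and % of deep sleep to the above model" and the team will "notice the reduction in magnitude of the above means contrasts". No interval, standard error, test or threshold is given for that reduction; the reference to statistical significance belongs to the earlier contrasts.

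On timing, the Study Overview says: "At baseline and 6 weeks, participants will undergo 48-hour ambulatory BP monitoring, in-home sleep study, complete a 3-day bladder diary". Sleep change and the BP and bladder changes therefore cover the same six weeks.

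On direction, the Introduction describes effects both ways. It says "Both elevated nighttime systolic blood pressure (SBP), and poor sleep disrupt the diurnal pattern of urine excretion", and then: "This increased frequency nighttime awakenings with nocturia, in turn, contributes to poor sleep and elevated nighttime SBP".

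**The concern.** The step conditions on variables measured after randomisation. Randomisation protects the contrasts before the sleep terms enter, but not the contrasts after, so the difference between the two is not by itself a measure of what sleep does. The baseline outcome is the only other covariate in this model, so other common causes of sleep change and outcome change are not dealt with. Measurement at the same two visits cannot show which change came first.

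The size of the change would also be read without any guide to its noise. The GLM procedure gives a standard error for each contrast, but not for the difference between two nested fits to the same participants.

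What is at stake is the account of sleep's role. The Study Overview says: "This pilot study will provide critical preliminary data regarding the relation between sleep and nighttime BP in seniors". A misleading account could carry into the planned larger trial.

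**Working it through.** **Inputs from the documents.** Three arms of 10. The base model has 4 parameters, leaving 30 − 4 = 26 residual degrees of freedom; with two sleep terms entered together, 30 − 6 = 24. The documents give no SD, effect size or sleep-outcome correlation, so there is no planned figure to reproduce.

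**Assumptions.** Residual outcome SD 1; within-arm SD of each sleep change 1, scored so that higher is better; treatment effect τ = 0.8 SD unless stated; within-arm sleep-outcome correlation ρ = 0.3, 0.5 or 0.7; direct BBTI effect on WASO d = 0 or 0.5 SD; no effect of sleep on the outcome. In (1) and (2) the second sleep measure is pure noise. That BBTI shifts sleep at all is consistent with the Introduction, which says that "brief behavioral treatment of insomnia (BBTI) significantly improves not only sleep but also self-reported nocturia among the elderly"; the amount is assumed.

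**General form.** Adjusted contrast = τ − ρ × (arm difference in sleep change).

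**(1) The outcome change drives the sleep change.** The arm difference in sleep is ρτ + d, so the proportional fall is ρ² + ρd/τ.

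| ρ | d = 0 (either treatment) | BBTI, d = 0.5 |
|---|---|---|
| 0.3 | 9% (0.80 to 0.73) | 0.09 + 0.1875 = 28% |
| 0.5 | 25% (0.80 to 0.60) | 0.25 + 0.3125 = 56% |
| 0.7 | 49% (0.80 to 0.41) | 0.49 + 0.4375 = 93% |

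The sign matters. At d = −ρτ, which is −0.40 SD for ρ = 0.5, there is no shrinkage; with a more negative d the contrast grows.

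**(2) An unmeasured cause drives both.** The arm difference in sleep is d, so the proportional fall is ρd/τ. With d = 0.5 for BBTI this is 19%, 31% and 44% (30%, 50% and 70% for τ = 0.5). With d = 0 for chronotherapy it is 0 on average. If the cause moves sleep and outcome in opposite directions, the contrast grows: at ρ = −0.5 it goes from 0.80 to 0.80 + 0.25 = 1.05.

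Simulation at 10 per arm matched the shrinkage figures in (1) and (2). At ρ = 0.5 they are the same with 50 or 100 per arm, so a larger sample does not remove them.

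**Other assumptions give other amounts.** If the outcome drives both sleep measures with coefficient 0.5, the contrast goes from 0.80 to 0.48. If a shared cause gives correlation 0.3 among outcome and both sleep measures, and BBTI shifts both measures by 0.8 SD, it goes from 0.80 to 0.43. True 50% mediation gives 0.80 to 0.41, nearly the same as the shared-cause case.

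**(3) Chance alone, 10 per arm.** With no sleep-outcome relation, the mean change is zero. The variance of the change is the sum over the two sleep measures of [(shift)² + 2/10] divided by 26 − 2 − 1 = 23, ignoring the small effect of baseline adjustment.

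- BBTI shifting both measures by 0.8 SD: 2 × (0.64 + 0.20)/23 = 0.073, SD 0.27. Simulation gives SD 0.27, a 95% range of about −0.56 to +0.57, and a fall of at least 20% in absolute size in 23–26% of trials (τ of 0.5 or 0.8).
- BBTI shifting both by 0.5 SD: 2 × (0.25 + 0.20)/23 = 0.039, SD 0.20; a fall of at least 20% in 18–22%.
- Chronotherapy, no shift: 2 × 0.20/23 = 0.017, SD 0.13; simulation gives 0.13–0.14, a range of about −0.29 to +0.29, and a fall of at least 20% in 12–17%.

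**(4) Would an interval be enough?** A within-arm percentile bootstrap 95% interval includes zero in 97–98% (BBTI) and over 99% (chronotherapy) of chance-only trials, so it deals with (3). Under the reverse path with d = 0.5, it excludes zero for BBTI in about 28% of trials at ρ = 0.5 and 57% at ρ = 0.7, although sleep mediates nothing. It does not deal with (1) or (2).

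**The case against.** The strongest reply is that the plan never claims mediation. It names no indirect effect, proportion mediated or causal conclusion, and hypothesis 1.1 is not spelled out, so the purpose of the step is inferred. That stands: a reader might infer that the sponsor intends a mediation claim, but the text does not say so. What remains is that looking for attenuation after adding sleep change has little other natural purpose.

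Second, this is a pilot that puts effect sizes ahead of p-values, and it promises inferential analyses in general, so an interval is unspecified rather than ruled out. That lowers the severity. It does not remove the point, because relying on magnitude makes the uncertainty of that magnitude more useful.

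Third, every scenario above sets the effect of sleep on the outcome to zero, while the Introduction says that poor sleep increases nighttime urine production. A reader might infer from the scenarios that sleep has no role. They do not show that, and the documents point the other way; the scenarios show only that a misreading is possible.

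Fourth, the amounts are all assumed. For BP, the stated route back to sleep is indirect, through urine production and nocturia, so one range of ρ may not suit every outcome. Nor do the contrasts always shrink: the sign conditions in (1) and (2) limit that. Both qualifications stand.

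**Conclusion.** The concern holds as a minor one. The plan gives no uncertainty for the change in the contrasts, and the change does not by itself measure sleep's role. If the outcome change drives the sleep change, the contrasts shrink unless the treatment has a large enough opposing direct effect on sleep. If an unmeasured cause drives both, the contrast of a treatment that shifts sleep is biased: downward when cause and treatment move sleep and outcome in the same helpful direction, upward otherwise. At 10 per arm, chance moves the contrasts either way.

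The amounts for the first two depend entirely on the assumed correlation and effects; the chance figures depend on the assumed shifts in sleep and treatment effect. That the contrasts can change without mediation does not depend on the particular values chosen.

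A reader might also infer that the tests of the two treatments are compromised. They are not: the contrasts used for hypothesis 1.1 come from the model without sleep terms. Only the reading of sleep's role, in an exploratory last step of a 30-person pilot, is at risk.

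**What to change.** Replace "notice the reduction in magnitude of the above means contrasts" with two sentences:

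- (a) *For each contrast we will report the difference between the estimates without and with the sleep terms, with a within-arm bootstrap 95% CI, as an exploratory analysis.*
- (b) *Because sleep and outcomes are measured at the same time points, may influence each other and may share unmeasured causes, these results show association only and cannot establish that sleep mediates the treatment effect.*

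(c) If the step is meant to cover all four listed outcomes, leave out PSQI, which is itself a sleep outcome.

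Item (a) deals with chance. Item (b) is needed as well, because the interval does not remove the bias.

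The cost is a few sentences and a short bootstrap program, with no new data. The downsides are a weaker mechanistic claim and wide, somewhat conservative intervals: under chance alone, the median width is about 1.2 SD for BBTI and 0.9 SD for chronotherapy.

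### The last analysis step compares treatment contrasts from two GLM fits that need not contain the same participants, so missing sleep data can pass for an effect of adjusting for sleep

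*Combined protocol and SAP*

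**What the plan says.** The Study Overview describes a pilot in which participants are "randomly assigned to one of the 3 groups of 10 participants each". Its measurements are listed together: "At baseline and 6 weeks, participants will undergo 48-hour ambulatory BP monitoring, in-home sleep study, complete a 3-day bladder diary". The listed outcomes come from the ambulatory BP monitor, the bladder diary and the PSQI.

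The Data Analysis section first specifies "analysis of covariance (ANCOVA) models using the SAS® GLM procedure with pre- to post-intervention change in each continuous outcome", with "BBTI (yes/no), chronotherapy (yes/no) and baseline value of outcome as independent variables". No sleep-change variable is in that model. The BBTI and chronotherapy contrasts against usual care from it are the test of hypothesis 1.1. The plan then says it will "add changes in measures of sleep (decrease in WASO) and % of deep sleep to the above model" and "notice the reduction in magnitude of the above means contrasts". The section also says that effect sizes will carry more weight than p-values.

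The documents define no analysis set, missing-data rule or expected dropout, and they do not require the two models to share participants. They also do not say which instrument supplies WASO or the percentage of deep sleep. The in-home sleep study is the likely source.

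**The concern.** The quantity read in the last step is a difference between two fitted contrasts. It can be attributed to the sleep variables only if nothing else changed between the fits.

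GLM omits any observation with a missing dependent or independent variable. The first model needs the outcome at both visits. The second also needs the WASO change and the deep-sleep measure (read here as a change too). A participant with usable BP or diary data but no usable sleep record at one visit is therefore in the first fit only. With 10 per arm, losing even one or two such participants can move a contrast by an amount similar to the reduction being sought.

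The plan does not call this a mediation analysis, but in substance it is one. It is also the only planned analysis that links change in sleep to the treatment effects, and the pilot is meant to inform a larger trial. Because magnitudes are read directly and no interval is planned for the difference, nothing in the output would show that the sample had changed.

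**Working it through.** The plan gives no effect size, SD, power or missingness rate, so there is no figure of its own to reproduce.

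**Inputs from the documents.** Three arms of 10 (Study Overview). First model: BBTI, chronotherapy, baseline outcome. Second model: the same plus two sleep variables (Data Analysis).

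**Assumptions, not in the documents.** True contrast 0.8 SD (0.5 SD as a variant). Sleep variables that are pure noise, so the true reduction is zero. All 10 per arm have the outcome, and *k* per arm also have sleep data, with *k* = 9, 8 or 7. A 20% fall counts as a visible reduction: 0.2 × 0.8 = 0.16 SD. Baseline–change correlation is 0 or 0.5.

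**Step 1: shift from dropped rows alone.** With random loss, the SD of (contrast on 10 vs 10 minus contrast on *k* vs *k*) is about √(2/*k* − 2/10) residual SDs:

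- *k* = 9: √(0.2222 − 0.2) = 0.149
- *k* = 8: √(0.25 − 0.2) = 0.224
- *k* = 7: √(0.2857 − 0.2) = 0.293

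If baseline correlates 0.5 with change, the residual SD is √(1 − 0.25) = 0.866, and these become 0.129, 0.194 and 0.254. Simulation in which each sleep record is lost independently with probability 10%, 20% or 30% gave 0.14, 0.22 and 0.29, with mean zero.

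**Step 2: the two parts of the difference.** At 10% missing, dropped rows contribute SD 0.142, and adjustment for noise covariates within common rows contributes 0.132. Together √(0.142² + 0.132²) = 0.194; the simulated total is 0.195. At 20% missing, √(0.219² + 0.158²) = 0.270, against 0.271 simulated.

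**Step 3: how often a spurious reduction of at least 20% appears.** Simulation, 6,000 to 8,000 trials per setting, 0.8 SD effect. The ranges mainly reflect the assumed baseline correlation.

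| Sleep data usable per arm | As planned | Both fits on common rows |
|---|---|---|
| 10 of 10 | about 6–9% | identical |
| 9 of 10 | 18–22% | 9–11% |
| 8 of 10 | 24–29% | 11–14% |
| 7 of 10 | 30–34% | 14–17% |

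False increases of the same size were as common: in one run, 22.7% increases against 21.5% reductions at 9 per arm. With a 0.5 SD effect, the planned comparison gave 28–39%, common rows 17–24%, and complete data about 15%.

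**Step 4: missingness related to response.** If active-arm participants with larger changes are more often missing, row dropping alone gives a mean false reduction of about 0.11, 0.19 and 0.27 SD at 10%, 20% and 30% missing. The chance of an apparent reduction of at least 20% of 0.8 SD is then 36%, 53% and 62%. As a simple check, losing the two largest of 10 values lowers an arm's mean by about 0.32 SD.

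**Step 5: after the fix.** On a common set the row-drop part is exactly zero. Only the adjustment noise remains, with SD about 0.13–0.16 at 10–20% missing.

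**The case against.** The strongest case is that this is a silence in a very short plan, not an error. Adding variables to a model is compatible with refitting both versions on common rows. The step has no threshold or decision rule, states no conclusion about mechanism, and sits in a 30-person pilot. This is fair, and it limits how serious the point is. It does not remove it: run as written in GLM, the two fits use whatever rows each can, and the difference between them is what gets read.

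Second, the size depends on a pattern the documents do not give. BP monitoring, sleep study and diary share the same two time points, so a participant who leaves before week 6 loses outcome and sleep data together and creates no mismatch. Only loss specific to sleep counts. If the only lost record is in the chronotherapy arm, the BBTI contrast hardly moves (row-drop SD 0.02; spurious reductions 9.5% against 9.2% with complete data). All of this stands, which is why the figures are a range under assumptions.

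Third, common rows are only a partial cure. Spurious reductions still occur in about 9–17% of null trials, and each contrast already has a standard error near √(2/10) = 0.45 SD. This also stands, and is why an interval for the change in contrast is needed as well.

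A reader might infer that the plan gives a wrong answer whenever a sleep study is missing, or that it is biased towards finding a role for sleep. The documents do not support either reading. Under random loss the shift averages zero and can hide a real reduction as easily as create a false one. A systematic false reduction needs missingness related to response, and nothing in the documents shows that.

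**Conclusion.** The point holds as a moderate one. The last analysis step can mix a change of sample into the quantity it reads, and nothing in the documents prevents this. Under the stated assumptions (0.8 SD effect, noise sleep variables, 1 to 3 per arm randomly lacking sleep data although the outcome is present), dropped rows add variation of about 0.13–0.29 SD. They raise the rate of spurious reductions to roughly twice that on common rows. The effect is zero if sleep data are complete, and directional only if missingness depends on response.

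The treatment contrasts that test hypothesis 1.1 come from the preceding step and are untouched. It would be wrong to infer that the trial's main comparisons are at risk. That the sleep measures come from the in-home sleep study is an inference, but the point does not depend on it: any source that can be missing separately from the outcome has the same effect.

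**What to change.** Add to the end of the Data Analysis section, for this exploratory step only:

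> For each outcome, the models with and without the sleep-change variables will both be fitted to participants who have the outcome and both sleep changes. Contrasts will be compared only within that set. The number of participants per arm will be reported for each fit, and the change in each contrast will be given with a bootstrap confidence interval. The main contrasts will continue to use all participants with the outcome.

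The common set removes the row-drop component exactly. The interval is needed because chance imbalance in the sleep variables remains on common rows, and with about 21 to 27 participants it will be wide. That width is itself useful information for the larger trial.

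The cost is a few sentences, one extra model run per outcome, a bootstrap, and slightly fewer participants in this comparison only. No data collection or clinical procedure changes.
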